5.1.4.3 Dose-Limiting Toxicity

A DLT is defined as a \geq Grade 3 adverse drug reaction (ADR) according to the NCI-CTCAE v4.0, occurring in the DLT evaluation period of the dose escalation cohorts. ADRs are defined in this trial as any AEs suspected to be related to avelumab by the investigator and / or Sponsor.

The observation period for DLTs refers to the first 3 weeks of trial drug treatment in the dose escalation part for all dose cohorts for all subjects with data used for implementing the dose-escalation algorithm for determination of the MTD. Additional subjects enrolled in the dose escalation phase will have AEs collected but will not have a specific DLT observation period. A DLT is defined as any \geq Grade 3 treatment-related toxicity confirmed by the SMC to be relevant for the study drug treatment. The SMC recognizes that in the absence of prior human experience with avelumab, a conservative approach will be adopted in ascribing the relevance of the treatment-related toxicity to drug. Treatment-related SAE will be ascribed as related to drug except where a clear relationship to the underlying disease or recognized co-morbidities is evident. For this trial, the MTD is defined as the highest dose where < 2 of 6 subjects experience a DLT.

A DLT is specifically defined as any one of the following:

Any Grade ≥ 3 toxicity that is possibly, probably, or definitely related to avelumab, occurring during the DLT evaluation period (21 days after administration of avelumab), except for any of the following:

- Grade 3 infusion-related reaction resolving within 6 hours and controlled with medical management.
- Transient (≤ 6 hours) Grade 3 flu-like symptoms or fever, which is controlled with medical management.
- Transient (≤ 24 hours) Grade 3 fatigue, local reactions, headache, nausea, emesis that resolves to \leq Grade 1.
- Grade 3 diarrhea, Grade 3 skin toxicity, or Grade 3 liver function test (ALT, AST, or GGT) increase that resolves to \leq Grade 1 in less than 7 days after medical management (e.g., immunosuppressant treatment) has been initiated.
- Single laboratory values out of normal range that are unlikely related to trial treatment according to the investigator, do not have any clinical correlate, and resolve to \leq Grade 1 within 7 days with adequate medical management.
- Tumor flare phenomenon defined as local pain, irritation, or rash localized at sites of known or suspected tumor.

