5.1.7.2 ADRs Requiring Treatment Discontinuation or Modifications

The following ADRs require permanent treatment discontinuation of avelumab:

Any Grade 4 ADRs require treatment discontinuation except for single laboratory values out of normal range that are unlikely related to trial treatment as assessed by the investigator, do not have any clinical correlate, and resolve within 7 days with adequate medical management.

Any Grade 3 ADRs require treatment discontinuation except for any of the following:

- Transient (≤ 6 hours) Grade 3 flu-like symptoms or fever, which is controlled with medical management.
- Transient (≤ 24 hours) Grade 3 fatigue, local reactions, headache, nausea, emesis that resolves to \leq Grade 1.
- Single laboratory values out of normal range (excluding \geq Grade 3 liver function test increase) that are unlikely related to trial treatment according to the investigator, do not have any clinical correlate, and resolve to \leq Grade 1 within 7 days with adequate medical management.
- Tumor flare phenomenon defined as local pain, irritation, or rash localized at sites of known or suspected tumor.
- Any Grade ≥ 3 drug-related amylase or lipase abnormality that is not associated with symptoms or clinical manifestations of pancreatitis does not require dose delay. The Study Medical Monitor should be consulted for such Grade ≥ 3 amylase or lipase abnormalities.
- Increases in ECOG performance status ≥ 3 , which do not resolve to ≤ 2 by cycle Day 14 of the following cycle (infusions should not be given on the following cycle, if the ECOG performance status is ≥ 3 on the day of study drug administration).

Any Grade 2 ADR should be managed as follows:

- Infusion should not be given in case of ongoing Grade 2 ADR on the day of trial treatment administration.
- Treatment can be resumed according to original schedule once ADR resolved to Grade ≤ 1 . Up to 2 subsequent study drug doses may be omitted. If more than two doses are skipped, treatment may be resumed after consultation with study Medical Monitor.
- Infusion-related reactions, hypersensitivity reactions (Grades 1 to 4), tumor lysis syndrome, and irAEs should be handled according to the guidelines provided in Sections [6.5.4.1](#), [6.5.4.2](#), [6.5.4.3](#), [6.5.4.4](#), respectively.

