8.4 Analysis Sets

The following analysis sets will be defined separately for the dose escalation part and the expansion cohorts in this trial, as applicable:

- **DLT population (dose escalation part):** all subjects with data used for implementing the dose-escalation schedule. These subjects should have received all study treatment administrations in the DLT evaluation period or should have stopped treatment because of DLTs in the DLT evaluation period.
- **Safety population:** all subjects who have received at least 1 dose of trial treatment.
- **Full analysis set (FAS):** all subjects who have received at least 1 dose of trial treatment.
- **PD-L1 positive FAS (urothelial carcinoma efficacy expansion cohort):** all PD-L1+ subjects who have received at least 1 dose of trial treatment.
- **PK population:** All subjects who have completed at least 1 infusion of study drug, and who have provided sufficient concentration measurements.
- **Efficacy population (efficacy expansion cohorts):** all subjects who have received at least 1 dose of trial treatment and have measurable disease at baseline according to IERC assessment.
- **PD-L1 positive efficacy population (urothelial carcinoma efficacy expansion cohort):** all PD-L1+ subjects who have received at least 1 dose of trial treatment and have measurable disease at baseline according to IERC assessment.

- **Efficacy population (primary and secondary expansion cohorts):** all subjects who have received at least 1 dose of trial treatment and have measurable disease at baseline according to investigator assessment.

The definition of the Safety Population and the FAS are identical in this non-randomized study; the Safety population will be used for the safety analysis and the FAS will be used for efficacy analysis. The PD-L1 positive FAS will be the primary analysis population for the primary endpoint of BOR by IERC in the urothelial carcinoma efficacy expansion cohort.

PD-L1 status is assessed by immunohistochemistry. Subjects will be considered PD-L1 positive (negative) for the urothelial carcinoma efficacy expansion cohort if at least (less than) 5% of the tumor cells show PD-L1 membrane staining, respectively. If during assay development (based on generic samples) a different cut-off is determined to be more appropriate, this cut-off may be adapted in the SAP prior to analysis of subject samples from this trial.

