8.5.2 Analysis of Primary Endpoints

8.5.2.1 Maximum Tolerated Dose Determination

For determination of the MTD, individual subject data from the dose escalation part will be reported.

In addition, for the final statistical analysis, the following will be analyzed:

- At each dose level, the number and proportion of subjects in the DLT population who experience a DLT during the first DLT evaluation period.
- At each dose level, the number and proportion of TEAEs experienced by subjects in the DLT population during the first DLT evaluation period.

The MTD will be determined according to the dose-escalation plan described in Section 5.1.4.2. The MTD is defined as the highest dose level at which no more than 1 subject out of 6 subjects treated in a cohort and evaluable for DLT determination experiences a DLT.

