	
48 hours between 2 subjects). This additional cohort will have the purpose of generating safety data, PK data and receptor occupancy data at the respective dose.
 
Definition of DLT
 
A DLT is specifically defined as any Grade ≥ 3 toxicity that is possibly, probably, or definitely related to avelumab, occurring during the DLT evaluation period (21 days after administration of avelumab), except for any of the following:
 
 • Grade 3 infusion-related reaction resolving within 6 hours and controlled with medical management. • Transient (≤ 6 hours) Grade 3 flu-like symptoms or fever, which is controlled with medical management. • Transient (≤ 24 hours) Grade 3 fatigue, local reactions, headache, nausea, emesis that resolves to \leq Grade 1. • Grade 3 diarrhea, Grade 3 skin toxicity, or Grade 3 liver function test (ALT, AST, or GGT) increase that resolves to \leq Grade 1 in less than 7 days after medical management (e.g., immunosuppressant treatment) has been initiated. • Single laboratory values out of normal range that are unlikely related to trial treatment according to the investigator, do not have any clinical correlate, and resolve to \leq Grade 1 within 7 days with adequate medical management. • Tumor flare phenomenon defined as local pain, irritation, or rash localized at sites of known or suspected tumor. 
DLTs requiring treatment discontinuation are described in Section 5.1.7.2 of Protocol Amendment 12.
 
Subjects who do not complete the DLT observation period for reasons other than a DLT will be replaced.
 
Expansion phase
 
This section was included into the Expansion SAP.

Number of Subjects
	
Dose escalation phase: 18 up to 60 subjects.
 
The final sample size, however, will depend on the total number of dose levels to be tested, and subject replacement for DLT evaluation if applicable.

Trial Product
	
Avelumab will be administered as a 1-hour (-10 minutes /+20 minutes, i.e., 50-80 minutes) i.v. infusion. Subjects will receive avelumab once every 2

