	
All subjects will have a subsequent visit scheduled 10 weeks after the last administration of avelumab. The visit will include a full assessment of safety parameters.
 
AEs will be documented until the end of treatment visit. After the end of treatment visit only treatment related AEs have to be documented until the post-treatment safety follow-up visit. Subjects with a serious AE ongoing at the post-treatment safety follow-up must be monitored and followed up by the investigator until stabilization or until the outcome is known, unless the subject is documented as “lost to follow-up”.
 
Subjects without progressive disease at the end-of-treatment visit will be followed up for disease progression (CT / MRI scans every 12 weeks) up to 1 year. In addition, subjects will be followed for any AE suspected to be related to trial treatment, especially for the occurrence of new autoimmune events up to 3 months after the last dose of avelumab.
 
After the end-of-treatment visit, subjects will be followed quarterly for survival (including assessment of any further tumor therapy). The survival follow-up will continue until 1 year after the last subject receives the last dose of avelumab.
 
For dose expansion cohorts
 
This section was included into the Expansion SAP.

Randomization and Blinding	Not applicable.

8 Overview of Planned Analyses

There will be one planned analysis after the end of dose escalation phase. This SAP will only address the analysis for the dose escalation phase. Additional SAPs for SMC analyses and for all other analyses (interim, primary, and final) for expansion cohorts have been developed separately.

9 Changes to the Planned Analyses in the Clinical Trial Protocol

The data cut-off date was changed to Nov 20, 2015 from 6 weeks after the last subject of the dose escalation part has received its first administration of avelumab in order to provide a more comprehensive evaluation of the dose escalation phase in the first interim CTR for this study.

10 Analysis Sets

The following analysis sets will be defined for the dose escalation part:

- Screening analysis set: all subjects who signed the informed consent form (ICF).
- DLT analysis set: all subjects with data used for implementing the dose-escalation schedule. These subjects should:
 - Have received all study treatment administrations during the DLT evaluation period (first 21 days of treatment) or

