 - Have stopped treatment because of DLTs during the DLT evaluation period.
- Safety (SAF) analysis set: all subjects who have received at least 1 dose of trial treatment.
- PK analysis set: all subjects who receive at least one dose of avelumab, and provide at least one measurable post-dose concentration.

Unless otherwise stated, DLT analysis set will be used for the summary of the incidence of DLT, and PK analysis set will be used for the PK analysis, other analyses including safety analyses will be based on SAF analysis set.

11 General Specifications for Statistical Analyses

- The endpoint data will be summarized by dose level and overall, unless otherwise specified.
- All data recorded during the study will be presented in individual data listings. Data collected after re-initiation of treatment will not be included for safety summaries except for disposition, but will be included in the data listings.
- All data will be evaluated as observed, and no imputation method for missing values will be used, unless otherwise specified.
- Duration will be calculated as stop date – start date + 1, unless otherwise specified.

-
- The first day (Day 1) of study treatment is defined as the day of the first administration of avelumab, unless otherwise stated. The last dose date of study treatment is defined as the day of the last administration of avelumab, prior to the re-initiation of study treatment if applicable.
 - Baseline is defined as the last non-missing observation prior to the administration of first dose of trial treatment. Additionally, baseline for HR and QT/corrected QT (QTc) assessments will be derived from the visit where both HR and QT are not missing. If duplicate or triplicate electrocardiograms (ECGs) are collected, baseline for each ECG measurement is the average of the pre-dose replicate measurements on the baseline day. QT interval correction based Fridericia's or Bazett's formula ($QTcF/QTcB$) will be derived based on HR and QT. The average of the replicate measurements should be determined after the derivation of the individual parameter at each time point.
 - If the laboratory assessments are not done for scheduled visit but they are available for unscheduled visit on Day 1 from a different laboratory, the unscheduled visit will be included for the derivation of baseline; if there are multiple non-missing assessments on Day 1, the assessment from scheduled visit will be used for the derivation of baseline.

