16.1 Primary Endpoint Analysis

The primary endpoint in the dose escalation part of this trial is the occurrence of DLTs during the DLT evaluation period.

A DLT is defined as a Grade ≥ 3 adverse drug reaction according to the NCI-CTCAE v4.0, occurring during the DLT evaluation period confirmed by the SMC to be relevant for the study drug treatment based on the criteria specified in Protocol.

The summary of DLTs will include the following variables by dose level and overall for the DLT analysis set:

-
- the number and percentage of subjects who experienced a DLT during the DLT evaluation period
 - number of DLT per subject, 1 /2 /≥3
 - DLT by SOC and PT

The number and percentage of subjects who experienced a TEAE by SOC and PT during the DLT evaluation period will also be summarized by dose level and overall for the DLT analysis set. A listing of DLT AEs will include dose level, subject identifier, SOC/PT, and all relevant variables, such as start/stop date, toxicity grade, relationship to the study treatment, outcome etc., from AE eCRF page.

The MTD or maximum dose will be determined according to the dose-escalation plan described in section 5.1.4.2 of trial protocol. The MTD or maximum dose is defined as the highest dose level at which no more than one out of 6 subjects treated in a cohort and evaluable for DLT determination experiences a DLT.

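### If a subject is withdrawn before the Day 15 dose for a Grade 3 reaction that is exempt from the DLT definition, the planned DLT-window TEAE table leaves that subject out; a companion table would close this minor reporting gap.

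*SAP*

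**What the plan says.** The number and percentage of subjects with a "TEAE by SOC and PT during the DLT evaluation period will also be summarized by dose level and overall for the DLT analysis set" (dose-escalation SAP 16.1). This carries out protocol 8.5.2.1, which asks at each dose level for "the number and proportion of TEAEs experienced by subjects in the DLT population during the first DLT evaluation period".

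Dose-escalation SAP section 10 gives two ways into the DLT set. The first of them reads "Have received all study treatment administrations during the DLT evaluation period (first 21 days of treatment) or", and the alternative route is worded "Have stopped treatment because of DLTs during the DLT evaluation period". Protocol 8.4 agrees: a subject without all doses in the window belongs only if the second route applies, "or should have stopped treatment because of DLTs in the DLT evaluation period".

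The DLT definition (protocol 5.1.4.3, repeated in SAP section 6) exempts a "Grade 3 infusion-related reaction resolving within 6 hours and controlled with medical management". It also exempts some events of a second kind, worded "Grade 3 diarrhea, Grade 3 skin toxicity, or Grade 3 liver function test (ALT, AST, or GGT) increase that resolves to"; the condition there is a return to Grade 1 or lower in under 7 days once management has begun.

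The discontinuation rule in protocol 5.1.7.2 is separate: "Any Grade 3 ADRs require treatment discontinuation except for any of the following". The list that follows contains neither of those exemptions, and its exception for isolated laboratory values specifically leaves out liver-test increases. Protocol 6.5.4.1 and Table 6.1 also end treatment for any Grade 3 infusion-related reaction, however short. Table 6.2 discontinues for Grade 3 diarrhea and for Grade 3 liver-test elevation. For Grade 3 rash it allows either delay or discontinuation.

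**The concern.** The list of events that are not DLTs and the list of Grade 3 reactions that do not end treatment differ. A subject can therefore lose treatment because of a drug reaction without having had a DLT. The DLT set has no place for such a subject when the reaction falls before the second dose.

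For a DLT table this follows from the definition. For a TEAE table it means that inclusion depends on the outcome being tabulated: the reaction that ended treatment also removes the subject from the summary. Safety and tolerability form the primary objective of the escalation phase. This is also the only planned summary of all TEAEs by dose level that is confined to the DLT window. With 3 to 6 subjects per dose level, one omitted toxicity withdrawal is visible.

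**Working it through.** **Tracing one subject.** Dosing is every 2 weeks, so Day 1 and Day 15 fall within the 21-day window. Suppose that after Day 1 a subject has a Grade 3 infusion reaction that resolves within 6 hours.

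1. It is not a DLT (5.1.4.3).
2. Treatment ends (5.1.7.2, 6.5.4.1, Table 6.1), so there is no Day 15 dose.
3. Not all doses were received and the stop was not for a DLT, so neither route into the DLT set applies.
4. Sections 5.1.4.3 and 5.5.1 replace subjects who do not complete the observation period for reasons other than a DLT. If the subject counts as not completing it, a replacement enters. If the subject is followed off drug to Day 21 and counts as completing it, there is no replacement, but the subject is still outside the set.

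The same trace holds for Grade 3 diarrhea or a Grade 3 liver-test rise that resolves in under 7 days. Rash is unclear because of Table 6.2. The exemptions for flu-like symptoms or fever, for fatigue-type events, for isolated laboratory values other than liver tests, and for tumor flare also appear among the 5.1.7.2 exceptions, so they do not force withdrawal.

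**Effect on the table.** Let x of n subjects in the DLT set have a term, and let k be left out. The table shows x/n. Among all entered, a term that the omitted subjects had is (x+k)/(n+k); a term that they did not have is x/(n+k).

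- Replaced, n=6, k=1: 0/6 shown against 1/7 = 14.3%; 1/6 = 16.7% against 2/7 = 28.6%.
- Replaced, n=3, k=1: 0/3 against 1/4 = 25.0%.
- Not replaced, cohort of 6: 0/5 against 1/6 = 16.7%.
- Term that the omitted subject did not have: 1/6 = 16.7% shown against 1/7 = 14.3%, slightly high.
- Term that every subject had: 6/6 against 7/7, so the percentage is unchanged and only the count is short.

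**How likely it is.** The documents state no rate for this event. The nearest figures are the related events leading to permanent discontinuation in the 10 mg/kg expansion (protocol 3.4).

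- Types named above: 6 infusion-related reaction + 3 GGT increased + 1 AST increased + 1 hepatocellular injury = 11. No related withdrawal for diarrhea or rash is listed.
- 11/480 = 2.3%. The printed percentages imply a smaller denominator (25 subjects printed as 6.6%, and 25/0.066 is about 379), which gives 11/379 = 2.9%.
- These cover all grades and all times. The event at issue must also be Grade 3, resolve quickly and precede Day 15.

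The chance of at least one such subject among n is 1 − (1 − q)^n, with q assumed:

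| q | n = 3 | n = 6 |
|---|---|---|
| 1% | 3.0% | 5.9% |
| 2.3% | 6.7% | 13.0% |
| 2.9% | 8.5% | 16.2% |

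Rates of 5% or 10% would give 26.5% or 46.9% among 6. But 25/480 = 5.2% is the rate of related withdrawals of every kind, so those values are at or above the total for all related causes.

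**The case against.** The SAP does what protocol 8.5.2.1 prescribes, and a companion to the DLT table naturally shares its denominator. TEAE number, severity and duration are secondary endpoints, which SAP 16.2 assigns to section 17.1 on the safety set. There the subject is counted: in the by-dose TEAE tables (17.1.1), in related TEAEs leading to discontinuation (17.1.2), and in infusion reactions by grade and by infusion of first onset (17.1.4). SAP 12.1 lists dosing dates, reason off treatment and the DLT-set flag by dose level. With up to 60 planned subjects, a case can be found by hand. No document says that such a subject existed.

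Most of this stands, and it is why the point is minor. What it leaves is that the safety-set tables run to last dose plus 30 days (SAP section 11). At 3, 10 and 15 or 20 mg/kg they may also include add-on subjects who have no DLT window. None of them gives window TEAEs for the subjects entered for DLT evaluation.

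A reader might infer that the DLT rate or the MTD is biased. The documents do not support that: under the definition as written the omitted subject had no DLT, and the MTD rule rests on evaluable subjects. A reader might also infer that the toxicity disappears from the report, or that every percentage in the window table is too low. The safety-set outputs rule out the first, and the 1/6 against 1/7 comparison rules out the second.

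**Conclusion.** The gap is real, conditional and minor. If a subject is withdrawn before Day 15 for a DLT-exempt Grade 3 reaction that ends treatment, the window TEAE table understates the count of subjects with events. It also understates the percentage for the terms that the subject had, unless that percentage is already 100%. Percentages for other terms read slightly high. One such subject means 0/6 in place of 1/7, or 0/5 in place of 1/6 without replacement.

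An assumed rate at or below about 3% per dosed subject is reasonable on the expansion figures, giving up to about a 16% chance of at least one among 6. That assumption carries expansion experience at 10 mg/kg over to escalation. Protocol 3.4 says that most of the infusion-reaction and anaphylactic-reaction withdrawals came before premedication became mandatory in January 2014. Escalation was planned to start in Q1 2013, so its rate could differ.

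**What to change.** In dose-escalation SAP 16.1:

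- Keep the DLT table on the DLT set, and keep the DLT-set version of the window TEAE table.
- Add beside it a window TEAE table (SOC and PT, by dose level) on all dosed subjects entered for DLT evaluation. Include those not evaluable or replaced, and exclude add-on subjects without a DLT window.
- Report by dose level the number not evaluable or replaced, with reason, event, grade and day.
- Record the addition in SAP section 9.

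Separately, the sponsor should reconcile the DLT exemptions (5.1.4.3), the discontinuation rules (5.1.7.2, Tables 6.1 and 6.2), the replacement rule (5.1.4.3, 5.5.1) and the DLT-set definition (protocol 8.4, SAP section 10), and state how they apply to these subjects. This review takes no view on which clinical rule is right.

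The cost is one flag for subjects entered for DLT evaluation and a few table rows from data already collected. At some dose levels the window summary may look less favorable.
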